10.1.6 Suspected Unexpected Serious Adverse Reaction

Adverse drug reactions are all untoward and unintended responses to an investigational product related to any dose administered. Unexpected adverse reactions are suspected unexpected serious adverse reaction (SUSARs) if the following three conditions are met:

- 1) The event must be serious;
- 2) There must be a certain degree of probability that the event is a harmful and an undesirable reaction to the medicinal product under investigation, regardless of the administered dose;
- 3) The adverse reaction must be unexpected, that is to say, the nature and severity of the adverse reaction are not in agreement with the product information as recorded in the IB for an IMP.

10.2 Causality of Adverse Events

Relationship (causality) to the IMP will also be assessed by the investigator. The relationship of each AE to the IMP, including solicited systemic ARs (solicited local (injection site) reactions are considered as related by default) will be assessed using the following categories:

Related:	There is suspicion that there is a relationship between the IMP and the AE (without determining the extent of probability); there is a reasonable possibility that the IMP contributed to the AE.
Not Related:	There is no suspicion that there is a relationship between the IMP and the AE; there are other more likely causes and administration of the IMP is not suspected to have contributed to the AE.

10.2.1 Relationship to Trial Procedures

Relationship (causality) to trial procedures should be determined for all AEs.

The relationship should be assessed as Cq if the investigator considers that there is a reasonable possibility that an event is due to a trial procedure. Otherwise, the q*o ^ L c v c *..Wqv^ q q..v^ v" b

10.2.2 Outcome of Adverse Events

Resolved:	The subject has fully recovered from the event or the condition has returned to the level observed at Baseline.
Resolving:	The event is improving but the subject is still not fully recovered.
Not resolved:	The event is ongoing at the time of reporting and the subject has still not recovered.
Resolved with sequelae:	As a result of the AE, the subject suffered persistent and significant disability/incapacity (e.g., became blind, deaf or paralysed).
Fatal:	The subject died due to the event. If the subject died due to other circumstances than the event, the outcome of the event per se should be stated otherwise (e.g., not resolved or resolving).
Unknown:	If outcome is not known or not reported.

10.4.4 Collection and Reporting of Serious Adverse Events

Collection of SAEs and AESIs will commence from the time that the subject is administered the dose of IMP (Day 0). Routine collection of SAEs and AESIs will continue until Day 365 for subjects in the main trial and Day 730 for subjects in the extension.

SAEs should be reported according to the following procedure:

A sponsor SAE form must be completed, in English, and signed by the investigator immediately or within 24 hours of first onset or notification of the event. The information should be completed as fully as possible but contain, at a minimum:

- i. A short description of the event and the reason why the event is categorized as serious.
- ii. Causality assessment.
- iii. Protocol number.
- iv. Subject identification number.
- v. 4L q "o name.

The SAE form should be transmitted within 24 hours to the safety mailbox or Fax:

e-mail: [contact]

Fax: [[name]]([contact])

10.4.4.1 Adverse Events of Special Interest

Any AESI occurring during the trial will be categorized and reported as an SAE. These AESIs include anaphylaxis, thrombocytopenia, and other pIMCs. [Appendix D](#) provides a list of pIMCs, which includes Guillain Barré syndrome.

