To assess the safety of IVX-A12 compared to placebo by describing the incidence of serious adverse events (SAEs), adverse events of special interest ([AESI], which are potential immune-mediated conditions [pIMCs]), medically-attended adverse events (MAAEs), LRTI cases of any severity (mild, moderate, severe) caused by RSV and/or hMPV (clinical event of special interest [CESI]), LRTI cases of any severity (mild, moderate, severe) not caused by RSV or hMPV, and adverse events (AEs) leading to trial withdrawal up to Day 365.	
 - SAEs, AESIs (which are pIMCs), MAAEs, and AEs leading to trial withdrawal up to Day 365 (end of main trial). - Mild, moderate, or severe LRTI cases caused by RSV or hMPV (CESI) up to Day 365. - Clinical safety laboratory parameters at screening, and Days 0, 7, and 28; - Mild, moderate, or severe LRTI cases not caused by RSV or hMPV up to Day 365.
Secondary Immunogenicity	
Objectives	Endpoints

 - To evaluate the serum NAb response to IVX-A12 or placebo at Day 0, Day 180, and Day 365. - To evaluate the serum IgG binding antibody response to IVX-A12 or placebo at Day 0, Day 180, and Day 365 after vaccination. - To evaluate the proportion of subjects \geq 2-fold increase in serum NAb and serum IgG binding antibody titers at Days 180 and 365 compared to baseline (Day 0). - To evaluate the proportion of subjects with an \geq 2-fold increase in serum NAb and serum IgG binding antibody titers at Days 28, 180 and 365 compared to baseline (Day 0). 	
 - GMT of RSV/A-, RSV/B-, hMPV/A-, and hMPV/B-specific NAb at Days 0, 180, and 365. - GMTs of RSV and hMPV prefusion F protein-specific IgG antibody titers at Days 0, 180, and 365. - Geometric mean fold increase (SRR) in serum anti-RSV/A-, RSV/B-, hMPV/A-, and hMPV/B-specific NAb from prevaccination/baseline (Day 0) to Days 180, and 365 after vaccination. - Proportion of subjects with an \geq 2-fold increase in serum anti-RSV/A-, RSV/B-, hMPV/A-, and hMPV/B-specific NAb from prevaccination/baseline (Day 0) to Days 28, 180, and 365 after vaccination. - Proportion of subjects with \geq 2-fold increase (SRR) in RSV- and hMPV prefusion F protein-specific IgG antibody titers from

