10.1.5 Serious Adverse Events

An SAE is defined as any untoward medical occurrence that at any dose meets any of the following criteria:

- 1) Results in death.
- 2) Is life-threatening (i.e., the subject was, in the opinion of the investigator, at immediate risk of death at the time of the event); it does not refer to an event that hypothetically might have caused death if it were more severe.
- 3) Requires in-patient hospitalization or prolongation of existing hospitalization.
- 4) Results in persistent or significant disability/incapacity (i.e., the event causes a substantial disruption of a subject's ability to conduct normal life functions).
- 5) Congenital anomaly or birth defect in the offspring of a subject.
- 6) An important and significant medical event that may not be immediately life-threatening or resulting in death or hospitalization but, based upon appropriate medical judgment, may jeopardize the subject, or may require intervention to prevent one of the other outcomes listed above.

AEs which do not fall into these categories are defined as non-serious.

It should be noted that a severe adverse event need not be serious in nature and that an SAE need not, by definition, be severe.

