3.1.3. Secondary Safety Objective

[figure not shown]
The secondary safety objective is to assess the safety of IVX-A12 compared to placebo by the incidence of serious adverse events (SAEs), adverse events of special interest (AESIs) (which were defined as potential immune-mediated conditions (pIMCs)), medically-attended adverse events (MAAEs), clinical event of special interest (CESIs) (which were defined as lower respiratory tract illness (LRTI) cases of any severity (mild, moderate, severe) caused by RSV and/or hMPV), LRTI cases of any severity (mild, moderate, severe) not caused by RSV or hMPV, and AEs leading to trial withdrawal up to Day 365 (end of the main trial).

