5.1.2. Secondary Endpoints

5.1.2.1. Safety Secondary Endpoints

- SAEs, MAAEs, AESIs (including pIMCs) and AEs leading to trial withdrawal up to Day 365 (end of the main trial);
- Mild, moderate, or severe LRTI caused by RSV and/or hMPV (CESI) up to Day 365;
- Clinical safety laboratory parameters at screening, and Days 0, 7, and 28;
- Mild, moderate, or severe LRTI cases not caused by RSV or hMPV up to Day 365.

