10.1.1.6. Adverse Events of Special Interest (AESI) and Potentially Immune-Mediated Disorders (pIMCs)

AESIs and pIMCs are AEs described by MedDRA preferred terms as defined in the protocol sections 10.4.4.1 and [section 16](#) of the SAP.

AESIs, up to end of the main trial, will be summarized by vaccine group, aggregate IVX-A12, and overall as follows:

- The number and percentage of subjects reporting AESIs by SOC and PT.
- The number and percentage of subjects reporting vaccine-related AESIs by SOC and PT

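### The SAE tables mix events that meet the seriousness criteria with AESIs and CESIs that are serious only by rule, and the AESI definition differs between sections

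*Protocol*

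**What the plan says.** On seriousness, Protocol 10.1.5 lists six criteria and adds that "AEs which do not fall into these categories are defined as non-serious". Protocol 10.4.4.1 then has any AESI both categorized and reported as an SAE. SAP 10.1.1.3 repeats the six criteria and follows them with a sentence under which CESIs, AESIs and pIMCs are all reported as SAEs. For CESIs, Protocol 10.4.3 requires an entry on the AE eCRF and a separate summary, and says nothing about SAE status. MAAEs, in Protocol 10.1.4 and SAP 10.1.1.4, exclude events that fulfil the seriousness criteria.

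On what an AESI is, the secondary safety objective in Protocol 2.0 and 5.0 refers to "adverse events of special interest ([AESI], which are potential immune-mediated conditions [pIMCs", and the matching endpoint reads "SAEs, AESIs (which are pIMCs), MAAEs, and AEs leading to trial withdrawal up to Day 365 (end of main trial". SAP 3.1.3 agrees: "which were defined as potential immune-mediated conditions (pIMCs". Protocol 10.4.4.1 is wider: "These AESIs include anaphylaxis, thrombocytopenia, and other pIMCs". SAP 5.1.2.1 is open-ended: "SAEs, MAAEs, AESIs (including pIMCs) and AEs leading to trial withdrawal up to Day 365 (end of the main trial". SAP 10.1.1 and 10.2.1 name anaphylaxis and thrombocytopenia alongside pIMCs. SAP 10.1.1.6, which governs the AESI tables, states that "AESIs and pIMCs are AEs described by MedDRA preferred terms as defined in the protocol sections 10.4.4.1 and" SAP Section 16.

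**The concern.** SAEs, AESIs, MAAEs and CESIs are all secondary safety endpoints. A reader of an SAE table expects the standard seriousness criteria. If the table also holds events placed there by rule, the SAE incidence is no longer the quantity that Protocol 10.1.5 defines, and it cannot be compared with SAE rates from trials that use only those criteria.

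The CESI part carries a further difficulty. RSV or hMPV LRTI is the illness the vaccine is meant to prevent, and it is the exploratory efficacy event in SAP 11.1.1. If the vaccine works, adding CESIs to the SAE count would raise the placebo SAE rate more than the active rates and flatter the safety comparison.

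The AESI wording matters less but affects the same tables. Two events named in the analysis text have no preferred terms, so the programmer must choose them.

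**Working it through.** **Step 1. The plan's own safety figure.** Protocol 13.4 and SAP 4.3.1 give the chance of seeing at least one affected subject among 100. The formula is 1 − (1 − p)^100.
- p = 1%: 1 − 0.99^100 = 63.4%.
- p = 2%: 1 − 0.98^100 = 86.7%.

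Both reproduce. The documents state no AESI, CESI or SAE rate.

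**Step 2. Seriousness, passage against passage.**

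| Event | Protocol 10.1.5 | Rule elsewhere |
|---|---|---|
| AESI meeting none of the six criteria | non-serious | SAE (Protocol 10.4.4.1; SAP 10.1.1.3) |
| Grade 1 CESI | non-serious unless a criterion is met | AE eCRF only (Protocol 10.4.3); SAE (SAP 10.1.1.3) |

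Neither row is empty by construction. Under Protocol 10.1.3 a Grade 1 CESI needs two mild lower respiratory symptoms for at least 24 hours, for example cough and sputum, plus RT-PCR confirmation. The pIMC list includes skin conditions such as vitiligo and alopecia areata, which need not meet any of the six criteria.

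The CESI row is also a difference between the two documents. SAP Section 12 lists four changes from the protocol, and this is not one of them. SAP 10.1.1.5 derives CESIs by program, so a site that followed the Protocol may never have completed an SAE form for an event the SAP calls an SAE.

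**Step 3. The MAAE table.** A rule-only SAE meets none of the criteria in 10.1.5, so on the wording of Protocol 10.1.4 it stays an MAAE if it led to an unscheduled visit. If its SAE label is taken as seriousness, it drops out. Protocol 10.1.3 obtains the confirming swab at an unscheduled trial visit, so the question could arise for many non-serious CESIs. Neither document answers it.

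**Step 4. AESI scope, passage against passage.**
- pIMCs only: the secondary safety objective and endpoint in Protocol 2.0 and 5.0, and SAP 3.1.3.
- Wider set: Protocol 10.4.4.1; SAP 10.1.1, 10.1.1.6 (by reference to 10.4.4.1) and 10.2.1.
- Term list (Protocol Appendix D, repeated in SAP Section 16): no anaphylaxis entry, and thrombocytopenia only in its autoimmune form.

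Protocol 10.4.4.1 also speaks of other pIMCs after naming the two events. That treats both as pIMCs, although the list does not carry anaphylaxis or unqualified thrombocytopenia.

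**Step 5. Size.** One reclassified subject moves an incidence by 1/100 = 1 percentage point in an active arm and 1/50 = 2 points on placebo. How many subjects are affected cannot be derived from the documents. As an illustration only, let p be an assumed share of subjects with an event whose placement depends on the rule or the definition. The chance of at least one such subject is 1 − (1 − p)^n.

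| Assumed p | n = 50 | n = 100 | n = 250 | Expected in 250 |
|---|---|---|---|---|
| 0.1% | 4.9% | 9.5% | 22.1% | 0.25 |
| 0.5% | 22.2% | 39.4% | 71.4% | 1.25 |
| 1% | 39.5% | 63.4% | 91.9% | 2.5 |
| 2% | 63.6% | 86.7% | 99.4% | 5 |

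**The case against.** The strongest reply is that treating AESIs as SAEs is a deliberate convention, stated in both documents, and that the sixth criterion of 10.1.5 (important medical events) already covers part of it. This stands as a reason to leave site reporting alone. It does not make an event serious when the investigator finds no criterion met, and it does not cover CESIs, where the Protocol states no such rule.

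A second reply is that the SAP sentence concerns reporting, not tabulation. That is possible. But the sentence stands in the section that specifies the SAE tables, and Protocol 10.4.4.1 speaks of categorization as well as reporting.

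A third is that little has happened in practice. Protocol 4.4 says that the Day 28 interim analysis found neither serious events nor CESIs. This is fair for the first 28 days; both are collected to Day 365.

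Three stronger readings are tempting, and the documents do not support them.
- A reader might infer that any mild platelet decrease becomes an AESI and so an SAE. Protocol 10.4.4.1 names thrombocytopenia without a grade or threshold. Table 9 grades platelet counts without linking any grade to AESI status, and the AE definition in 10.1.1 gives a clinically significant laboratory finding as its example. The scope is undefined; it is not stated to be all grades, and no platelet-based count can be derived.
- A reader might infer that the AESI table depends on a free choice between passages. SAP 10.1.1.6 cites Protocol 10.4.4.1 together with Section 16, so the operative set is the wider one. What is missing is its terms.
- A reader might infer a live effect on the stopping rule for vaccine-related SAEs. That rule pauses vaccination, each subject receives one dose, and the Protocol describes enrolment as complete.

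**Conclusion.** The concern holds as a conflict in how the secondary safety tables are defined. Followed as written, the SAE table contains events that Protocol 10.1.5 calls non-serious. The extension to CESIs appears only in the SAP and is not declared as a change from the protocol. The effect on the MAAE table is undetermined. The mismatch in the AESI definition is real but narrower: the analysis text points to the wider set, and the gap is in the objectives, the Protocol endpoint and the term list.

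The size is 1 percentage point per subject in an active arm and 2 on placebo, assuming the planned 100 and 50 subjects. The number of subjects is unknown, and the table above rests on assumed rates. The SAE effect also depends on what sites entered on SAE forms, not on programming alone. Solicited reactions and the primary immunogenicity endpoints are unaffected. For the terminated extension only listings are planned, so there the AESI scope affects a listing.

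**What to change.** - Leave expedited reporting of AESIs unchanged.
- In the SAE tables, count events that meet Protocol 10.1.5. Show events that are SAEs only through Protocol 10.4.4.1 or SAP 10.1.1.3, CESIs included, on a separate line.
- State that the MAAE exclusion follows the 10.1.5 criteria, so a rule-only SAE can still be an MAAE.
- Reconcile the CESI sentence in SAP 10.1.1.3 with Protocol 10.4.3, or list it in SAP Section 12.
- Reconcile the AESI definition across the objectives, endpoints, Protocol 10.4.4.1 and the SAP analysis sections. The choice of definition is the sponsor's.
- Add to SAP Section 16 the preferred terms the sponsor intends for anaphylaxis and thrombocytopenia. In the AESI table show the pIMC list, anaphylaxis and thrombocytopenia on separate lines.

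The cost is SAP wording, a longer term list and a small amount of re-tabulation, with no new data. SAP Section 12 shows that the tables, listings and graphs had already been completed once, so the SAP should record that this change came after outputs were first produced.

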10.5 Follow-up Procedures

10.5.1 Adverse Events

All AEs will be monitored until resolution, or a stable status is reached or until a formal diagnosis can be made or until the end of the trial, whichever occurs first. If the subject is unwilling to undergo the remaining trial procedures (e.g., blood draw[s] or visits), they should be asked whether they agree to continue participating for safety reasons.

10.5.2 Serious Adverse Events

If information not available at the time of the first report becomes available later, the investigator should complete a follow-up SAE form or provide other written

documentation immediately. Copies of any relevant data from the hospital notes (e.g., laboratory tests, discharge summary, postmortem results) should be sent to the sponsor/sponsor designee, after redaction for privacy. All SAEs should be followed up until resolution, permanent outcome of the event, or is otherwise explained. The timelines and procedure for follow-up reports are the same as those for the initial report.

10.5.3 Safety Reporting to Investigators, Independent Ethics Committees or Investigational Review Boards, and Regulatory Authorities

The sponsor or designee will be responsible for the reporting of all SUSAR and any other SAEs to regulatory authorities, investigators, and IEC/IRB, as applicable, in accordance with national regulations in the countries where the trial is conducted. Relative to the first awareness of the event by/or further provision to the sponsor or designee, SUSARs will be submitted within 7 days for fatal and life-threatening events and 15 days for other SUSARs, unless otherwise required by national regulations. The sponsor or designee will also prepare an expedited report for other safety issues where these might materially alter the current benefit-risk assessment of an investigational vaccine or that would be sufficient to consider changes in the IMP administration or in the overall conduct of the trial. The trial site will also forward a copy of all expedited reports to their IEC/IRB in accordance with national regulations.

10.5.4 Post-trial Events

Any SAE that occurs after the end of the trial but is considered to be caused by the IMP must be reported to the sponsor. These SAEs will be processed by the L v v L v.q "Lqq v c o U o N " " o L N q v . q o U q L b A L N ^ L v B v how to submit these SAEs are included on the SAE form.

11.0 TRIAL-SPECIFIC REQUIREMENTS

The following sections provide information on the trial-specific requirements.

11.1 Stopping Rules

Monitoring of safety signals will be performed throughout the trial by an independent SMC. The clinical trial will be halted if there is clear evidence of potential harm or harmful effects. Vaccine administration may be paused for further review and assessment if any of the following events occur:

- In any trial subject:
 - Any death that could be related to vaccine as per the investigator, sponsor, or SMC chair occurring during the trial;
 - Any vaccine-related SAE during the trial;
 - Any life-threatening (Grade 4) vaccine-related AE/AR during the trial, which needs medical intervention including:
 - Ulceration, abscess or necrosis at the injection site;
 - Laryngospasm, bronchospasm, or anaphylaxis within 24 hours after administration of vaccine.
 - An allergic or hypersensitivity reaction such as fever >40°C or generalized urticaria (defined as occurring at three or more body parts) within 72 hours after administration of vaccine.
- If 2 or more subjects in a single trial group experience the same severe (Grade 3) AE/AR (Preferred Term [PT] in a given Medical Dictionary for Regulatory Activities [MedDRA] system organ class [SOC]) within the first 7 days following vaccination that persists for at least 48 hours and cannot be clearly attributed to another cause:
 - Severe (Grade 3) vaccine-related solicited local (injection site) reactions (excluding measured grades of erythema and swelling alone) or systemic AR;
 - Severe (Grade 3) vaccine-related unsolicited AE during the trial;
 - Severe (Grade 3) vaccine-related vital sign(s) abnormality;
 - Severe (Grade 3) vaccine-related clinical laboratory abnormality.

In the case that a pre-defined safety signal is met in any trial group, subsequent dosing will be halted to permit a complete evaluation of the reported event(s), and to consult the SMC. Based on the review of the data, the SMC may recommend temporary or permanent stopping, or continuation of dosing. When dosing resumes after a halt, further measures for safety may be introduced.

11.2 Safety Review Committee and Safety Monitoring Committee

An independent SMC will be constituted to monitor the safety of all subjects enrolled in the trial, including solicited local (injection site) reactions, solicited systemic ARs, unsolicited AEs, and clinical laboratory data. The SMC will review safety data collected during the 7 consecutive days following vaccination for all subjects, focusing on the interpretation of solicited local (injection site) reactions and solicited systemic ARs, unsolicited AEs, and clinical laboratory data in the first week after dosing when most reactogenicity is expected to occur.

Details of the membership, roles, and functioning of the committee will be available in the SMC charter.

12.0 DATA HANDLING AND RECORD KEEPING

The full details of procedures for data handling will be documented in the data management plan. AEs, medical history, and concurrent medical conditions will be coded using MedDRA. Drugs will be coded using the World Health Organization Drug Dictionary.

12.1 Electronic CRFs

Completed eCRFs are required for each subject.

The site will maintain adequate source documents for the recording and collection of subject data. Data will be entered into an EDC system. The sponsor will make arrangements to train appropriate site staff in the use of the EDC for completing the eCRFs. These forms are used to transmit the information collected in the performance of this trial to the sponsor and regulatory authorities. The eCRFs must be completed in English.

The principal investigator (or designee) must review the eCRFs for completeness and accuracy and must sign and date the appropriate eCRFs as indicated.

Furthermore, the investigator must retain full responsibility for the accuracy and authenticity of all data entered on the eCRFs.

The eCRFs will be reviewed for completeness and acceptability at the trial site during periodic visits by trial monitors. The sponsor or designee will be permitted to review the eCRFs for accuracy of the eCRFs. The completed eCRFs are the sole property of the sponsor and should not be made available in any form to third parties, except for authorized representatives of appropriate governmental health or regulatory authorities, without written permission of the sponsor.

